11.3 Secondary Objectives

11.3.1. To evaluate changes in platelets and hemoglobin from pre-op to post-op level for patients randomized to receive perioperative TXA versus placebo.

Summary statistics will be provided for the changes in platelet level and decline in hemoglobin from pre-op to post-op level, for both the TXA and placebo group. Two sample t-test or Wilcoxon rank sum test will be used to compare the differences between the two groups. Multiple comparison correction might be used for p-values to address the multiple testing issues due to measurements at multiple time points.

11.3.2. To evaluate differences in post-operative daily surgical drain output for patients randomized to receive perioperative TXA versus placebo.

Summary statistics will be provided for postoperative daily surgical drain output (in milliliters per 24 hour period for the duration of the drain) for each group. The group difference will be compared using two-sample t-test or Wilcoxon rank sum test depending on the distribution of the observed data. Multiple comparison correction might be used for p-values to address the multiple testing issues due to measurements at multiple time points.

11.3.3. To evaluate changes in estimated blood loss (EBL) for patients randomized to receive perioperative TXA versus placebo.

The EBL for pre-op to post-op level, for both the TXA treated group and placebo group will be estimated with a two-sided 95% confidence interval. The EBL of the two groups (TXA vs. Placebo) will be evaluated using a two-sample t-test or Wilcoxon rank sum test depending on the distribution of the observed data.

11.3.4. To evaluate the association between the intra-or post-operatively transfused blood volume and estimated blood loss (EBL) for patients randomized to receive perioperative TXA and placebo, respectively.

Regression model will be used to access the correlation between the log transformed intra-or post-operatively transfused blood volume and EBL.

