1.2 Secondary Objectives

1.2.1. To evaluate changes in platelets and in hemoglobin from pre-op to post-op level for patients randomized to receive perioperative TXA versus placebo.

- Study endpoint: changes in platelets and in hemoglobin from pre-op to post-op level, continuous measurement.

1.2.2 To evaluate differences in post-operative daily surgical drain output for patients randomized to receive perioperative TXA versus placebo.

- Study endpoint: postoperative daily surgical drain output, continuous measurement, for the duration of the drain.

1.2.3. To evaluate changes in estimated blood loss (EBL) for patients randomized to receive perioperative TXA versus placebo.

- Study endpoint: estimated blood loss, continuous measurement.

1.2.4. To evaluate the association between the intra-or post-operatively transfused blood volume and estimated blood loss (EBL) for patients randomized to receive perioperative TXA and placebo, respectively.

- Study endpoint: intra- or post-operatively transfused blood volume, continuous measurement, until resumption of chemotherapy; estimated blood loss (EBL), continuous measurement.

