6.2.10 Incisional healing

6.2.10.1. Presence or absence of dehiscence

6.2.10.2. Presence or absence of clinically significant hematoma

6.2.11 Functional Assessment

6.2.11.1. All patients enrolled on the study will receive a standard physical therapy evaluation at the same timepoints (with a window of +/- 2 weeks for all):

- weeks post-operatively
- 3 months post-operatively
- 6 months post-operatively

6.2.11.2 Additionally, during each physical therapy evaluation, participants will complete the FMA, PROMIS, and ROM assessment of the lower extremities.

6.2.11.3 See Appendix V.

Please see the table below for more detail and obtain other tests as needed for good patient care.

REQUIRED EVALUATIONS, TESTS, AND OBSERVATIONS

STUDIES TO BE OBTAINED	Pre-Op	In surgery/PACU/ Post-op	End of Study
History	X	with each outpatient visit	X
Physical Exam (Ht, Wt, BSA, VS, BMI)	X	with each outpatient visit	X
Type and screen	X		
CBC with differential, platelets	X	In PACU; daily while inpt; 1 week post-op	X
Urinalysis	X		
ROTEM		X In PACU	
Transfusions (amount in cc)		X	
Drain output (amount in cc)		X, daily until pulled	
Incisional healing (visualization)		X Post-op	X
Estimated Blood Loss		X At conclusion of surgery	
CMP	X	In surgery; daily while inpt; post-op day 3; 1 week post-op	X
Wound f/u		Daily until hospital discharge. At week 1 +/- 4 d for all pts; Every 10-14 days +/- 4 d for "high risk" participants; Every 7-10 days +/- 4 d for wounds undergoing active management of problems; At 6,12 weeks +/- 2 wks. for "low risk" participants; All pts. at 2 & 3 months +/- 3 wks.	X
PT, INR, PTT, fibrinogen	X	PACU; Inpt; 1 week post-op	X
Pregnancy Test*	X		
Physical therapy attendance	X	Inpt, 1, 2, 4 and 6 weeks post op +/- 2 wks; 2 and 3 mos. post op +/- 2 wks	X
Functional Mobility Assessment (FMA)		6 wks., 3 mos. post op +/- 2 wks	X
PROMIS	X	6 wks., 3 mos. post op +/- 2 wks	X
ROM	X	6 wks., 3 mos. post op +/- 2 wks	X

* The St. Jude IRB requires that a female patient of childbearing potential must have a negative pregnancy test as a condition of clinical research eligibility.

Obtain other studies as needed for good patient care. End of study for each participant will be after the 6-month evaluation (+/- 1 month) has been completed.

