11. STATISTICAL CONSIDERATIONS

11.1 Sample Size Consideration and Randomization

This study will be conducted as a randomized, placebo-controlled double-blind trial of the administration of TXA vs. placebo prior to a limb salvage procedure. The primary objective will be to evaluate if TXA will reduce the proportional blood transfusion volume and EBL. The sample size is calculated based on the hypothesis that the TXA administration will reduce the average total volume of red blood cell transfused per kilogram of body weight by 40% relative to the average total volume of red blood cells transfused of the placebo group. Our historical data should be representative of our proposed placebo group, and historically, the average total red blood cell volume transfused per kilogram of body weight is $19.78 \text{ mL/kg} \pm 11.38$. The distribution of the intra-or post-operatively transfused blood volume is normally distributed after $\log(1+x)$ transformation (mean=2.906, sd = 0.507). We use the two-sample t-test with unequal variances to access the primary objective through the $\log(1+x)$ transformation of proportional blood transfusion volume.

We calculate the sample size with the two-sided two-sample t-test with unequal variances for the $\log(1+x)$ transformation proportional blood transfusion volume. Nineteen patients in each group are sufficient to detect a 40% decrease of $\log(1+x)$ transformation of proportional blood transfusion volume (mean=2.435, sd = 0.488) with 0.8 power and type I error 0.05. It can be safely assumed that the number of patients who

do not require blood transfusion is less than 5%. Given the sample size, we do not anticipate the blood transfusion volume will have substantial ties at 0.

Randomization will be performed in the SJCRH Pharmaceutical Services Department by a pharmacist using the randomization program developed by the Department of Biostatistics.²⁶ The drug is clear and will be given IV. The people who would determine the transfusion volume are blinded to the treatment. The randomization is stratified by the variable pre-operative weight that leads to two strata: pre-operative weight > 45.2 kg and pre-operative weight <=45.2 kg, where 45.2 kg is the median of pre-operative weight in the historical control data underwent limb-sparing tumor resections of the proximal tibia or distal femur. The assignment ratio of the TXA group to the placebo group is 1:1.

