APPENDIX I: SCHEDULE OF EVALUATIONS

Schedule of Study Evaluations										
Event	Pre-OP	PACU	1-6 days (if inpt)	1 week	2 weeks	4 weeks	6 weeks	2 months	3 months	6 months
CBC, Differentials, Platelets	x	x	x	x						x
ROTEM		x								
Drain Output		x	x	x						
Wound f/u		x	x	x	x	x	x	x	x	x
Physical Therapy Attendance	x		x	x	x	x	x	x	x	x
CMP	x		x	x						x
PT, PTT, INR, Fibrinogen	x	x	x	x						x
History	x		x	x	x	x	x	x	x	x
Physical (Ht, Wt, BSa, VS, BMI)	x		x	x	x	x	x	x	x	x
Type and Screen	x									
Urinalysis	x									
Pregnancy Test	x									
FMA							x		x	x
PROMIS	x						x		x	x
ROM	x						x		x	x
EBL		x								
Evaluation for Adverse Events		x	x	x	x	x	x	x	x	x

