APPENDIX VI: RELATION OF STUDY ENDPOINTS TO PROTOCOL OBJECTIVES

Item	Pre-OP	PACU	1-6 d Post-OP	1 wk. Post-OP	2 wks. Post-OP	4 wks. Post-OP	6 wks. Post-OP	2 mos. Post-OP	3 mos. Post-OP	6 mos. Post-OP
Objectives 1.1.1 & 1.2.3 & 1.3.2: Amount of Blood transfused/ placebo arm		X	X							
Objectives 1.1.1 & 1.2.3 & 1.3.2: Amount of Blood transfused/ TXA- treatment arm		X	X							
Objectives 1.2.1: Platelet changes/placebo arm	X	X	X	X						
Objective 1.2.1: Platelet changes/TXA-treatment arm	X	X	X	X						
Objective 1.2.1: Hemoglobin changes/ placebo arm	X	X	X	X						
Objective 1.2.1: Hemoglobin changes/ TXA-treatment arm	X	X	X	X						
Objective 1.2.2: Drain output/placebo arm		X	X	X						
Objective 1.2.2: Drain output/ TXA-treatment arm		X	X	X						
Objectives 1.2.3 & 1.2.4 & 1.3.2: EBL/placebo arm (includes sponge counts + other measures during surgery)			X							
Objectives 1.2.3 & 1.2.4 & 1.3.2: EBL/TXA treatment arm (includes sponge counts + other measures during surgery)			X							
Physical Therapy Attendance (could relate to obj 1.3.1)	X		X	X	X	X	X	X	X	X
Objective 1.3.1: FMA							X		X	X
Objective 1.3.1: PROMIS	X						X		X	X
Objective 1.3.2 ROTEM		X								
Objective 1.3.3 Wound f/u placebo arm (as needed)		X	X	X	X	X	X	X	X	X

Objective 1.3.3 Wound f/u TXA-treatment arm (as needed)		X								
---	--	----------	----------	----------	----------	----------	----------	----------	----------	----------

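### Section 11.3.1 fixes no time point for the platelet and hemoglobin comparison, leaves multiplicity correction optional, and does not adjust for the pre-op value

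*Combined protocol and SAP*

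**What the plan says.** Objective 1.2.1 (section 1.2) has two endpoints, described as "changes in platelets and in hemoglobin from pre-op to post-op level, continuous measurement". No section says which post-op measurement is meant.

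For the analysis, section 11.3.1 says: "Two sample t-test or Wilcoxon rank sum test will be used to compare the differences between the two groups". It then adds: "Multiple comparison correction might be used for p-values to address the multiple testing issues due to measurements at multiple time points". It names no correction method, family of tests, baseline covariate or longitudinal model. Sections 11.3.2 and 11.3.3 let the choice between the t-test and the Wilcoxon test depend on the observed distribution; 11.3.1 gives no rule.

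The evaluation table in section 6.2 schedules the post-op blood count as "In PACU; daily while inpt; 1 week post-op", and again at end of study. Appendix I shows the inpatient days as days 1 to 6, only for patients still in hospital. Appendix VI has rows for this objective, such as "Objectives 1.2.1: Platelet changes/placebo arm", marked at pre-op, PACU, days 1 to 6 and 1 week, but not at 6 months.

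**The concern.** With several post-op measurements and no key one named, the sentence on correction makes sense only if more than one time point may be tested. The number of tests, the family they form and whether any correction applies are then all open. The same data could support a positive or a negative statement on this objective, depending on a choice that the plan allows to be made after the results are known. Blinding of treatment during the trial does not prevent that.

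Two further issues follow from the same paragraph. The pre-op count is collected for everyone but is used only by subtraction, which is generally less precise than using it as a covariate. And daily counts exist only while a patient is in hospital, so tests on later days would compare shrinking groups selected by length of stay, which is itself an outcome after randomization.

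**Working it through.** **1. The plan's own figure.** The documents give no error rate or test count for the secondary objectives. The nearest stated figure is the primary sample size in section 11.1: 19 per arm, with "mean=2.435, sd = 0.488) with 0.8 power and type I error 0.05", by a two-sided unequal-variance t-test. The placebo mean and SD on the log(1+x) scale are 2.906 and 0.507.
- Difference: 2.906 − 2.435 = 0.471.
- Standard error: √[(0.507² + 0.488²)/19] = 0.161.
- Power from the noncentral t distribution: 0.810 at 19 per arm and 0.788 at 18.

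The figure reproduces. I use 19 per arm below.

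**2. Number of tests** (section 6.2 table, Appendices I and VI).
- Days 1 to 6 counted as one visit: 1 PACU + 1 + 1 at one week = 3 points; × 2 analytes = 6 tests.
- Each inpatient day counted: 1 + 6 + 1 = 8 points; × 2 = 16 tests.
- Adding the 6-month count would give 18, but Appendix VI does not link that visit to this objective.

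**3. Chance of at least one false positive, uncorrected.** If the tests were independent, 1 − 0.95^k gives 0.26 for 6 tests and 0.56 for 16. They are not independent, since they share patients and a baseline. With pre/post correlation r and post/post correlation p, and equal variances, two change scores from one patient correlate at (1 + p − 2r)/[2(1 − r)]. This is 0.5 when p = r, and 0.86 when r = 0.3 and p = 0.8. All these correlations are assumptions.

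Simulation (20,000 null trials, 19 per arm, complete data, each test at 0.05, analytes independent):

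| Points per analyte | Correlation of change scores | One analyte | Both |
|---|---|---|---|
| 3 | 0.5 | 0.13 | 0.24 |
| 3 | 0.8 | 0.10 | 0.19 |
| 3 | 0.86 | 0.09 | about 0.17 |
| 8 | 0.5 | 0.25 | 0.44–0.45 |
| 8 | 0.7 | 0.19 | 0.35 |
| 8 | 0.8 | 0.16 | 0.29 |
| 8 | 0.86 | 0.14 | 0.25–0.27 |

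The last column follows from the third as 1 − (1 − x)². If the two analytes correlate at 0.5, the value for both at change-score correlation 0.5 falls slightly, to about 0.42 (8 points) and 0.22 (3 points). Change-score correlations above 0.86 give lower values still: with 3 points, r = 0.3 and p = 0.9, about 0.15.

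**4. Cost of correcting across all points.** A standardized difference of 0.93 has 80% power at 0.05 with 19 per arm. With Bonferroni over 8 tests (0.05/8 = 0.00625) power falls to 0.50, and over 16 (0.05/16 = 0.0031) to 0.40. The optional correction therefore matters in both directions.

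**5. Baseline adjustment against change scores.** With equal pre-op and post-op variance s², a change score has variance 2s²(1 − r) and the adjusted value s²(1 − r²). The ratio is (1 + r)/2.

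| r (assumed) | Variance ratio | Standard error smaller by |
|---|---|---|
| 0.3 | 0.65 | 19% |
| 0.5 | 0.75 | 13% |
| 0.7 | 0.85 | 8% |
| 0.9 | 0.95 | 3% |

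If the post-op SD is k times the pre-op SD, the ratio becomes k²(1 − r²)/(1 + k² − 2kr). For k = 1.4 it is 0.84, 0.94 and 1.00 at r = 0.3, 0.5 and 0.7. For k = 0.7 it is 0.42, 0.47 and 0.49. It never exceeds 1, apart from the one degree of freedom spent.

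**The case against.** The case on the other side has five parts.
- **The plan does not say that it will test each day.** This is correct. Section 11.3.1 speaks of a post-op level, and testing by time point is inferred from the sentence on correction. A reader might infer a plan for 16 tests. The documents do not support that: 16 needs a separate test on each of six inpatient days, and the appendix columns can equally be read as 3 points.
- **The error rates depend on assumptions.** This also stands. The upper figure needs eight complete points and a change-score correlation of 0.5. If post-op values track each other more closely than they track the pre-op value, the rate is lower. The independence figure of 0.56 should not be used. Even so, most plausible settings leave the rate well above 0.05.
- **A two-sample test on change is valid under randomization, and the endpoint is defined as change.** True. A reader might infer bias, but the issue is precision only. The documents give no pre/post correlation, so its size cannot be settled from them. Adjusting for the pre-op value still estimates the arm difference in change.
- **The objective is secondary.** The primary test and its sample size do not depend on it, and no decision in the documents rests on 11.3.1.
- **The same sentence on correction recurs in 11.3.2, 11.4.1 and 11.4.3, with a variant for ROTEM in 11.4.2.** This favors settling all of them together, but it does not repair 11.3.1.

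**Conclusion.** The concern holds in a limited form. For a named secondary objective, the plan leaves the time point, the family of tests and the use of correction open, and it leaves a baseline that is already collected out of the model. The schedule allows 6 to 16 tests. Uncorrected, the chance of at least one false positive across both analytes is roughly 0.17 to 0.45, for change-score correlations of 0.5 to 0.86, complete data and independent analytes. The gain from baseline adjustment is about 3% to 19% in standard error for r from 0.9 to 0.3 if pre-op and post-op variances are equal. It can be larger, or close to nothing, if they differ. None of this bears on the validity of the change-score test or on the primary analysis. It deserves correction because it is cheap to put right before unblinding and cannot be put right convincingly afterwards.

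**What to change.** In section 11.3.1, replace the separate tests by one baseline-adjusted analysis per analyte:
- Use either ANCOVA at one post-op time point or a repeated-measures model (arm, day, arm-by-day), with the pre-op value as covariate. For repeated measures, state the covariance structure and a small-sample degrees-of-freedom method, given about 38 patients and up to 8 visits.
- Take one contrast per analyte, over a time point or window that the sponsor fixes before unblinding. Preferably choose one when nearly all patients are still in hospital, to limit selection by discharge. The documents point to no particular window.
- Apply Holm across the two analytes (first step 0.05/2 = 0.025). Two uncorrected tests would still give 1 − 0.95² = 0.0975 if independent.
- Report other days as estimated differences with confidence intervals and no p-values.

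The same amendment can replace the optional wording on correction in 11.3.2 and 11.4.1 to 11.4.3 with a definite rule.

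The cost is a paragraph of SAP text and a standard model, with no new data. Day-specific p-values are given up and one degree of freedom is spent. A repeated-measures model also assumes that counts missing after discharge can be explained by the observed values, another reason to prefer an early window.

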6.2.6 Post-op coags

6.2.7 ROTEM

6.2.8 Management of drain and drain output

- 6.2.8.1. Drain emptied and recorded at discharge from PACU
- 6.2.8.2. Measured and recorded when drainage collection system bag is full and/or every 8 hours.
- 6.2.8.3. Drains will be placed to Hemovac or Somavac collection system. "Wall suction" will not be utilized.
- 6.2.8.4. Daily measurement of drain output will be tabulated (over a 24 and 48-

hour period)

6.2.8.5. Negative pressure wound therapy (if used) “output” will be measured and recorded per routine.

6.2.8.6. Patient to remain on antibiotics while drain is in.

6.2.8.7. Drains will be pulled when output is 75 ml or less per 24- hour period

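### If daily drain output is tested among drains still in place, as section 11.3.2 implies but does not state, the 75 mL removal criterion selects patients on the outcome and can understate a TXA effect after day 1 or, if the effect is short-lived, reverse it

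*Combined protocol and SAP*

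**What the plan says.** Section 1.2.2 defines the endpoint as "postoperative daily surgical drain output, continuous measurement, for the duration of the drain". Section 11.3.2 carries this into the analysis: "Summary statistics will be provided for postoperative daily surgical drain output (in milliliters per 24 hour period for the duration of the drain"), by group. It continues: "The group difference will be compared using two-sample t-test or Wilcoxon rank sum test depending on the distribution of the observed data". It then adds: "Multiple comparison correction might be used for p-values to address the multiple testing issues due to measurements at multiple time points".

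Section 6.2.8 sets out how the data arise:

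- 6.2.8.1: "Drain emptied and recorded at discharge from PACU".
- 6.2.8.2: "Measured and recorded when drainage collection system bag is full and/or every 8 hours".
- 6.2.8.4: "Daily measurement of drain output will be tabulated (over a 24 and 48" hours).
- 6.2.8.7: "Drains will be pulled when output is 75 ml or less per 24- hour period".

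The evaluations table in section 6.2 collects output each day until the drain comes out. Appendices I and VI schedule it in PACU, on days 1 to 6 and at 1 week. These entries cover collection and do not list tested days. Section 11.3.2 does not say which days are tested, whether a removed drain counts as zero, missing or a total, or whether the 24- and 48-hour figures are the tested variable. The missing proportions promised in 11.4.1 to 11.4.3 are not promised for drain output.

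**The concern.** Under 6.2.8.7, a patient's output on one day decides whether there is a value on the next. The wording of 11.3.2 (the life of the drain, the observed data, several time points) reads most naturally as a comparison on each day among drains still in place. From day 2 on, that comparison includes only patients whose earlier output exceeded 75 mL, and treatment may affect that condition. Section 2.2 cites reduced drain output as part of the case for TXA.

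If TXA works, more TXA drains leave early and the TXA patients still measured are the heavier drainers of their arm. Randomization then no longer protects the later-day comparisons. A lasting effect would be understated. An effect confined to the first day or two could make TXA look worse on the next day, which a reader might take for fading or rebound. The endpoint is not powered, so the main harm is a misleading estimate of a named secondary outcome rather than a lost test.

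**Working it through.** **The plan's figures.** The documents give no mean, SD, effect or power for drain output, so there is no drain figure to reproduce. The group size of 19 comes from the primary endpoint in section 11.1 and does reproduce. With log(1+x) means 2.906 and 2.435 and SDs 0.507 and 0.488, the unequal-variance t-test has power 0.788 at 18 per group and 0.810 at 19.

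**Inputs.** From the documents: the 75 mL per 24 h threshold and 19 per arm. Assumed: lognormal daily output, a placebo day-1 mean, a constant daily decay factor, between- and within-patient SDs on the log scale, and a 30% TXA reduction.

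**Closed form (300 mL, x0.6 per day, no within-patient variation).** Let M be an arm's mean on the previous day and s the between-patient log SD.

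- Share in place = Φ((ln(M/75) − s²/2)/s).
- Inflation of the mean among drains in place = Φ((ln(M/75) + s²/2)/s) ÷ share in place.
- Observed ratio = true ratio × TXA inflation ÷ placebo inflation.

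Day 3, s = 0.6, s²/2 = 0.18:

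- Placebo: M = 300 × 0.6 = 180 and ln(180/75) = 0.8755. Share in place = Φ(0.6955/0.6) = Φ(1.159) = 0.877. Inflation = Φ(1.759)/0.877 = 0.961/0.877 = 1.096.
- TXA: M = 0.7 × 180 = 126 and ln(126/75) = 0.5188. Share in place = Φ(0.3388/0.6) = Φ(0.565) = 0.714. Inflation = Φ(1.165)/0.714 = 0.878/0.714 = 1.230.
- Observed ratio = 0.70 × 1.230/1.096 = 0.786, a 21.4% reduction instead of 30%.

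| Log SD | In place on day 3, placebo v TXA | Observed reduction, day 2 | Day 3 | Day 4 |
|---|---|---|---|---|
| 0.4 | 98% v 86% | 29.6% | 25.5% | 15.7% |
| 0.6 | 88% v 71% | 27.0% | 21.4% | 14.5% |
| 0.9 | 70% v 55% | 22.8% | 18.3% | 13.8% |

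If the 30% reduction applies on days 1 and 2 only, the true day-3 ratio is 1 but the selection is the same. For s = 0.6 the observed ratio is 1.230/1.096 = 1.122, so TXA looks about 12% worse with no true difference.

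**Range of assumptions.** Simulation of 200,000 patients per arm in each of 81 combinations: day-1 mean 200, 300 or 450 mL; daily factor 0.60, 0.65 or 0.70; between-patient log SD 0.4, 0.6 or 0.9; within-patient log SD 0, 0.15 or 0.25. The drain is removed after the first day at 75 mL or less, and means are taken among drains in place.

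| Scenario | SD 0.4 | SD 0.6 | SD 0.9 |
|---|---|---|---|
| (a) True 30% every day: observed, day 2 | 26–30% | 22–29% | 19–26% |
| (a) day 3 | 18–30% | 16–27% | 15–23% |
| (a) day 4 | 9–28% | 10–24% | 11–20% |
| (b) Effect on days 1–2 only: TXA looks worse on day 3 by | 0–17% | 4–20% | 10–22% |
| (c) Effect on day 1 only: TXA looks worse on day 2 by | 0–5% | 1–10% | 6–16% |

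With no TXA effect, the result stays within 0.8 points of zero. The 24-hour output has no selection, because the criterion needs a full 24-hour output. The 48-hour total to removal leans toward TXA by about 0–2 points in (a) and 0–3.5 points in (c), because counting stops at removal.

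**Different assumptions, same pattern.** With a day-1 median of 300 mL, x0.6 per day, log SDs 0.5 between and 0.3 within patients, and a constant true ratio of 0.70, the in-place ratio on days 1 to 5 is 0.70, 0.72, 0.75, 0.81 and 0.86. With a median of 200 mL, x0.7 per day, and true ratios of 0.6 on day 1, 0.8 on day 2 and 1 afterwards, it is 1.09 on day 3.

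**Power at 19 per arm** (t-test on log output, true 30% reduction, 300 mL, x0.6, within-patient SD 0.25). For s = 0.6 the total log SD is √(0.36 + 0.0625) = 0.65. The noncentrality is 0.357/(0.65 × √(2/19)) = 1.69 on 36 df, which gives day-1 power 0.38. For SD 0.4, 0.6 and 0.9:

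- Day 1: 0.62, 0.38 and 0.21.
- 48-hour total: 0.67, 0.38 and 0.21.
- Day 3 among drains in place: 0.44, 0.19 and 0.09.

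**The case against.** The strongest reply is that the plan never states an analysis restricted to drains in place. The only reporting windows it fixes are the 24 and 48 hours of 6.2.8.4. Two windows would account for the mention of several time points, and that sentence recurs almost verbatim in 11.3.1, 11.4.1 and 11.4.3. On that reading the 24-hour value is free of selection, a 48-hour total is nearly so, and the day-3 and day-4 figures never arise. This has force: what is certain is a missing definition. It does not settle the matter, because 6.2.8.4 describes tabulation while 1.2.2 and 11.3.2 both refer to the life of the drain.

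Three further points stand as limits:

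- **Reversal.** With a constant effect, the expected result is only attenuation. Reversal in expectation needs an effect that wanes or is confined to the early days, which the documents neither state nor exclude.
- **Size.** The volumes are assumed, so the combinations show a range and carry no likelihoods. The bias is negligible when output is far above 75 mL and spread is low (450 mL, SD 0.4). Real drains are also recorded 8-hourly and need not come out exactly at day boundaries.
- **Noise.** With 19 per arm and log SDs of 0.6 and 0.25, the 95% interval for a day-1 ratio is roughly the estimate times 0.65 to 1.53. That is wide against a day-2 bias of a few points, and no false benefit arises from the in-place comparison when TXA has no effect.

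**Conclusion.** The concern holds, conditionally. If 11.3.2 is carried out as a daily comparison among drains in place, every day after the first is conditioned on earlier output. Whenever TXA lowers drainage, that selection works against TXA. Under the assumptions shown, a true 30% reduction on every day reads as 19–30% on day 2, 15–30% on day 3 and 9–28% on day 4. An effect limited to days 1 and 2 makes TXA look 0–22% worse on day 3. These sizes depend on volumes and spreads that the documents do not give. Day 1, the primary endpoint and the case of no TXA effect are unaffected. The point is a modest one on an unpowered secondary endpoint, but it is worth correcting because the data for an unselected estimate are already collected.

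**What to change.** Amend 1.2.2 and 11.3.2 before unblinding:

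1. Base the between-arm test on one fixed-window value per patient, in all evaluable randomized patients. The suggestion is to test the 24-hour output and report the 48-hour cumulative output as supportive. The reverse is acceptable if a longer window is wanted.
2. State when the window starts, whether the PACU volume of 6.2.8.1 is included, and that a drain removed within the window contributes its total to removal.
3. Show later daily output descriptively by arm, with the number of drains still in place each day and no formal tests. Report time to drain removal as supportive.

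The removal criterion itself is not questioned. The cost is a small wording amendment with no new data. The drawbacks are that later days lose their formal test and that a 24-hour test would miss an effect appearing only afterwards. The gain is an estimate not selected on the outcome, and one test in place of several whose correction is optional. It does not make the endpoint well powered: the 24-hour test has power of only about 0.2–0.6 for a 30% reduction.
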